#### 8.4.2. Contraception and Pregnancy

All WOCBP and all men (if their sexual partners are WOCBP) must use at least two methods of contraception, at least one of which is considered highly effective, during the study and 90 days after the final dose of study drug (for subjects in Part A and Part B) or 4 months after the final dose of study drug (for subjects in Part C), if heterosexually active. A woman is considered as a WOCBP (fertile) following menarche and until becoming postmenopausal unless permanently sterile. Permanent sterilization methods include total hysterectomy and/or bilateral salpingectomy and/or bilateral oophorectomy. A postmenopausal state is defined as no menses for 12 months without an alternative medical cause. A high follicle-stimulating hormone (FSH) level in the postmenopausal range may be used to confirm a postmenopausal state in women not using hormonal contraception or hormonal replacement therapy. However, in the absence of 12 months of amenorrhea, a single FSH measurement is insufficient. A man is considered fertile after puberty unless permanently sterile by bilateral orchiectomy.

Highly effective methods of contraception include the following:

- Combined (containing estrogen and progestogen) hormonal contraception associated with inhibition of ovulation. Delivery may be oral, intravaginal, or transdermal.
- Progestogen-only hormonal contraception associated with inhibition of ovulation. Delivery may be oral, injectable, or implantable.
- Intrauterine device
- Intrauterine hormone-releasing system
- Bilateral tubal ligation or occlusion
- Bilateral vasectomy (provided that the male has a medical assessment of surgical success)
- True sexual abstinence (defined as refraining from heterosexual intercourse during the entire period of risk, in line with the preferred and usual lifestyle of the subject)

All female subjects of childbearing potential will receive a pregnancy test (serum or urine) at screening and a negative result must be confirmed before the first dose in each cycle of treatment. If a subject becomes pregnant while participating in the study, she will be discontinued from study drug immediately. The early termination and safety follow-up visits will be scheduled and the pregnancy will be reported to Alkermes. Pregnancies in female partners of male subjects should also be reported and will be followed in the same manner. Additional follow-up may be required.

In the event of a pregnancy, a Pregnancy Report Form must be submitted to Alkermes (fax number in Section 13.5) within 24 hours of awareness of the pregnancy, irrespective of whether an AE has occurred. The pregnancy will be followed until completion or termination. If the outcome of the pregnancy meets the criteria for classification as an SAE it should be reported following the SAE procedure (see Section 13.5).

#### 8.4.3. Concomitant and Prohibited Medications

All intercurrent medical conditions will be treated at the discretion of the Investigator according to acceptable community standards of medical care. All concomitant medications and treatments will be documented on the eCRF.

The following treatments are not permitted during the study:

- Any other investigational treatment
- Any other systemic antineoplastic therapy including, but not limited to, cytotoxic chemotherapy, immunotherapy, targeted agents, hormonal therapy (except luteinizing hormone-releasing hormone antagonists or agonists for prostate cancer started at least 3 months before Cycle 1, Day 1 of ALKS 4230) or monoclonal antibody therapy
- Radiotherapy, including systemically administered radioisotopes; only palliative radiotherapy to a nontarget lesion is allowed at the discretion of the Medical Monitor

- Hematopoietic growth factors. In Part A, hematopoietic growth factors are prohibited during the DLT evaluation period. At all other times in Part A, and at all time in Parts B and C, hematopoietic growth factors may be used as clinically indicated.
- Pharmacologic doses of corticosteroids (greater than 10 mg of prednisone daily, or equivalent); topical, ophthalmological, and inhalational corticosteroids are permitted. Use of glucocorticoids for the purpose of treating immune-mediated AEs is permitted (see Section 9.8) but may result in discontinuation from study based on consultation between the Investigator and the Medical Monitor.

Medroxyprogesterone or megestrol acetate may be given to subjects without breast cancer as an appetite stimulant and bisphosphonates or denosumab may be administered to subjects with bone metastases if started 60 days before study entry.

As ALKS 4230 is a protein, there are no anticipated metabolic drug-drug interactions.

#### 8.4.3.1. Premedication

Antipyretics are required throughout the ALKS 4230 treatment period. To reduce the potential for infusion-related fever or chills, premedication with an antipyretic agent (nonsteroidal anti-inflammatory drugs and acetaminophen) is required at least 15 minutes prior to ALKS 4230 administration and should continue for at least 12 hours after the last dose of ALKS 4230 unless the Investigator has a rationale to withhold it from the subject.

# 8.5. Definition of End of the Study

A subject will have fulfilled the requirements for study completion if/when the subject has completed all study periods, including the Safety Follow-up Period and Follow-up Assessments or the last scheduled visit as indicated in the Schedule of Assessments (Table 5, Table 6, Table 7, and Table 8).

The end of the study will be the last subject's last visit (if applicable, the last phone call with the Investigator during the Safety Follow-up Period and Follow-up Assessments) as indicated in the Schedule of Assessments (Table 5, Table 6, Table 7, and Table 8).

# 8.6. **Protocol Deviations**

Should a protocol deviation occur, the Sponsor must be informed as soon as possible. Protocol deviations and/or violations and the reasons they occurred will be included in the clinical study report. Reporting of protocol deviations to the Institutional Review Board (IRB) or independent ethics committee and in accordance with applicable Regulatory Authority mandates is an Investigator responsibility.
# 9. TREATMENT OF SUBJECTS

## 9.1. Study Drug Dose and Administration

#### 9.1.1. ALKS 4230 Dosing and Administration

ALKS 4230 will be administered IV as a 30-minute infusion through a 0.22 µm in-line filter for 5 consecutive days, followed by a period off treatment in repeating cycles. During Cycle 1 of Parts A and B, the period off treatment will be 9 days, resulting in a cycle length of 14 days (2 weeks). Cycle 2 and subsequent cycles will have a period off treatment of 16 days, resulting in a cycle length of 21 days (3 weeks) for each cycle. Infusion for each dosing day of each cycle should begin within 3 hours (plus or minus) of the infusion start time for Day 1 of that cycle. Emergency resuscitation equipment should be available. For the first 2 treatment cycles of Part A, ALKS 4230 will be administered inpatient in a medical facility with access to medical support measures and to the intensive care unit, if needed. Subjects may be discharged on Day 6 of each of the first 2 treatment cycles if medically stable. In the absence of DLTs, subsequent treatment cycles may be administered on an outpatient basis. For Part B and Part C of the study, administration of ALKS 4230 may be done in an outpatient setting

In Part C, on days where ALKS 4230 is administered in combination with pembrolizumab, ALKS 4230 should be administered as an infusion  $60 (\pm 30)$  minutes after the completion of pembrolizumab infusion. For Part C, a subject's ALKS 4230 dose may be reduced by one dose level as needed at the discretion of the Investigator. Study drug dose adjustments for all subjects are described in Section 9.6.

Sites should make every effort to target infusion timing to be as close to 30 minutes as possible. However, given the variability of infusion pumps from site to site, a window between -5 minutes and +10 minutes is permitted (ie, infusion time is 30 minutes [-5 minutes/+10 minutes]).

ALKS 4230 may be infused using peripheral or central venous access per local standards of care and the treating Investigator's judgment. All subjects should have adequate intravenous access to allow the immediate management of toxicities. Subjects who do not have adequate peripheral venous access should have a central venous access device placed per local standards of care.

Amount of drug administered is based on subjects' body weight as measured at Day 1 (-72 hours) of each cycle.

Sites must have written procedures in place detailing the healthcare personnel required to be on site during subject dosing, the availability of equipment and medications necessary to treat an emergency (should it occur) and the process for transferring a subject to a medical facility if necessary.

#### 9.1.2. Pembrolizumab Dosing and Administration

Pembrolizumab is to be administered as an IV infusion over 30 minutes in a dose of 200 mg every 3 weeks, for up to 2 years as long as subjects are deriving clinical benefit (ie, objective response or SD), in accordance with the prescribing information (Keytruda [pembrolizumab] USPI). Subjects will be monitored for at least 1 hour for potential acute reactions to pembrolizumab prior to administration of ALKS 4230, as described in Section 9.1.1.

Sites should make every effort to target infusion timing to be as close to 30 minutes as possible. However, given the variability of infusion pumps from site to site, a window between -5 minutes and +10 minutes is permitted (ie, infusion time is 30 minutes [-5 minutes/+10 minutes]).

Pembrolizumab is to be obtained from the study sites' pharmacies, from commercial supplies or provided by Sponsor in countries where pembrolizumab is not yet approved.

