#### Investigational Product, Dosage, Duration, and Mode of Administration:

Reconstituted ALKS 4230 is administered via a 30-minute IV infusion once daily for 5 consecutive days, followed by 9 days off for Cycle 1 (Parts A and B) and 16 days off for all subsequent cycles.

In Part C, on days where ALKS 4230 is administered in combination with pembrolizumab, ALKS 4230 should be administered by infusion 60 ( $\pm$ 30) minutes after the completion of pembrolizumab infusion.

Pembrolizumab is to be administered as an IV infusion over 30 minutes in a dose of 200 mg every 3 weeks.

Sites should make every effort to target infusion timing to be as close to 30 minutes as possible for either drug. However, given the variability of infusion pumps from site to site, a window between -5 minutes and +10 minutes is permitted for ALKS 4230 and pembrolizumab (ie, infusion time is 30 minutes [-5 minutes/+10 minutes]).

Pembrolizumab is to be obtained from the study sites' pharmacies, from commercial supplies, or provided by Sponsor.

**Duration of Treatment:** In Parts A and B, Cycle 1 consists of 5 consecutive days of treatment with ALKS 4230 followed by 9 days off treatment, for a total of 14 days. Cycle 2 and all subsequent cycles of treatment consist of 5 consecutive days of treatment with ALKS 4230 followed by 16 days off treatment, for a total of 21 days for each cycle. Subjects may continue additional cycles of treatment until evidence of progressive disease, intolerance to ALKS 4230, removal by the Investigator, withdrawal of consent, or any other criteria for study removal.

In Part C, all cycles of treatment consist of pembrolizumab administration every 3 weeks in combination with 5 consecutive days of treatment with ALKS 4230 followed by 16 days off treatment, for a total of 21 days for each cycle. Subjects may continue additional cycles of treatment until evidence of progressive disease, intolerance to ALKS 4230, removal by the Investigator, withdrawal of consent, or any other criteria for study removal. For Part C, subjects who discontinue one drug (eg, due to unacceptable toxicity that cannot be managed by dose modification) must discontinue the entire study treatment.

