# Table 7:Schedule of Assessments and Study Visits - Part C

Procedure	Screen- ing		(2		YCLI .YS/C		E)			(2	C 1 DA	YCLI YS/C		LE)			EXT	ENS	ION	STAH PHA CYCI	SE ?			Safety	
Day	(D-21 to	1	2	3	4	5	8	15	1	2	3	4	5	8	15	1	2	3	4	5	8	15		Follow -up	Up Assess-
Window (days)							+2	+1						+2	+1						+2	+1	EOT a	Period	
Informed consent	Х																								
Eligibility criteria review	Х																								
Demographics and medical history	Х																								
Physical examination b	Х	Х							Х							Х							Х		
Airway evaluation c	Х	Х							Х							Х							Х		
Vital signs d	Х	Х	Х	Х	Х	Х	Х		Х	Х	Х	Х	Х	Xe		Х	Х	Х	Х	Х			Х		
Weight and height f	Х	Х							Х							Х									
ECOG performance score	Х	Х					Х		Х						Х	Х							Х		
12-lead ECG g	Х	Х				Х			Х							Х							Х		
Hematology h,i	Х	Х		Х		Х	Х		Х		Х		Х	Xe	Х	Х				Х			Х		
Biochemistry h	Х	Х		X		Х	Х		Х		Х		Х	Xe	Х	Х				Х			Х		
TSH h	Х								Х							Х							X		
Serum tumor markers j	Х								Х							Х									
Coagulation panel h	Х	Х					X		Х							Х							X		
Pregnancy test k	Х	Х							Х							Х							X		
Urinalysis h	Х	Х					X		Х							Х							X		
Tumor imaging 	Х														Х							Х			X m
Administration of ALKS 4230 n		Х	х	X	x	X			Х	x	x	X	x			х	х	Х	x	x					

Procedure	Screen- ing (D-21 to D1)		(2	-	YCLI YS/C	E 1 CYCL	E)			(2	-	YCLI YS/C	E 2 EYCL	E)		_	EXT	ENS	ION	STAF PHA CYCI	SE 3		EOT a	Safety Follow -up Period	Follow- Up Assess- ments
Administration of Pembrolizumab		Х							Х							х									
PK sampling°		Х	Х	Х	Х	Х			Х	Х	Х	Х	Х			Х		Х		Х					
Immunophenotype sampling p		Х	Х	Х	Х	Х	Х	Х	Х	Х	Х	Х	Х	Х	Х	Х				Х					
Cytokine sampling q		Х	Х	Х	Х	Х			Х	Х	Х	Х	Х												
Immunogenicity sample r		Х							Х							Х							Х		
Archival tumor tissue sample s	Х																								
Tumor biopsy t	Х													Х											
ctDNA u	Х						Х		Х							Х							Х		
Prior and concomitant medications v	Х	Х	х	х	Х	х	х	х	X	Х	Х	Х	Х	Х	Х	X	Х	х	х	Х	Х	x	X		
Adverse events u,i	Х	Х	Х	Х	Х	Х	Х	Х	Х	Х	Х	Х	Х	Х	Х	Х	Х	Х	Х	Х	Х	Х	X	Xw	

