#### Table 7: Schedule of Assessments and Study Visits - Part C (Continued)

Abbreviations: ANC=absolute neutrophil count, ECG=standard 12-lead electrocardiogram, ECOG=Eastern Cooperative Oncology Group, EOT=end of treatment, IFN=interferon, IL=interleukin, INR=international normalized ratio, iRECIST=Immune Response Evaluation Criteria in Solid Tumors, NK=natural killer, PK=pharmacokinetic, RECIST=Response Evaluation Criteria in Solid Tumors, TNF=tumor necrosis factor, TSH=thyroid-stimulating hormone.

\* For procedures beyond 1 year of treatment (ie, after Cycle 18) please refer to the Schedule of Assessments of the Extension Phase (Table 8). The subjects who are already beyond 1 year of treatment will enter the Extension Phase immediately and will start following the Schedule of Assessments of the Extension Phase.

a End-of-treatment assessments must be completed for all subjects. Once subjects have completed the EOT visit, subjects will be followed for the Safety Follow-up Period.

b Comprehensive physical examination to be done at screening and EOT. Brief physical examination focused on areas of disease or adverse events to be done on Day 1 of all treatment cycles.

c Airway evaluation to be done at times of the physical exam. Subjects with head and neck cancer only. See Section 8.3.7.1 for details of the Screening Airway Evaluation and Section 8.3.7.2 for details of the On Study Airway Evaluation.

d In Cycle 1 and Cycle 2, Day 1 vital signs should be collected before pembrolizumab infusion, during pembrolizumab infusion and at end of pembrolizumab infusion. Vital signs should also be collected before ALKS 4230 infusion; during the infusion; at end of infusion; and 0.5, 1, 2, 3, 4, and 6 hours (±15 minutes) after ALKS 4230 infusion. During all other dosing days of Cycle 1 and Cycle 2, vital signs should be collected before ALKS 4230 infusion; during the

- infusion; at end of infusion; and 0.5, 1, 2, 3, 4, and 6 hours ( $\pm 15$  minutes) after ALKS 4230 infusion. On dosing days in Cycles 3 and beyond, vital signs are to be collected before pembrolizumab infusion; middle of ALKS 4230 infusion; end of ALKS 4230 infusion; and 0.5, 1, and 2 hours ( $\pm 15$  minutes) after ALKS 4230 infusion. Blood pressure, pulse, and respiratory rate should be measured after the subject has been resting in a seated or supine position for at least 5 minutes. Section 8.3.6 for further details.

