3.8. ADMINISTRATION OF STUDY DRUG

3.8.1. ALKS 4230 Dosing and Administration

ALKS 4230 will be administered IV as a 30-minute infusion

for 5 consecutive days, followed by a period off treatment in repeating cycles. During Cycle 1 of Parts A and B, the period off treatment will be 9 days, resulting in a cycle length of 14 days (2 weeks). Cycle 2 and subsequent cycles will have a period off treatment of 16 days, resulting in a cycle length of 21 days (3 weeks) for each cycle. Infusion for each dosing day of each cycle should begin within 2 hours (plus or minus) of the infusion start time for Day 1 of that cycle. Emergency resuscitation equipment should be available. For the first 2 treatment cycles of Part A, ALKS 4230 will be administered inpatient in a medical facility with access to medical support measures and to the intensive care unit, if needed. Subjects may be discharged on Day 6 of each of the first 2 treatment cycles may be administered on an outpatient basis. For Part B and Part C of the study, administration of ALKS 4230 may be done in an outpatient setting.

In Part C, on days where ALKS 4230 is administered in combination with pembrolizumab, ALKS 4230 should be administered as an infusion 60 (± 30) minutes after the completion of pembrolizumab infusion. For Part C, a subject's ALKS 4230 doses may be reduced by 1 dose level as needed at the discretion of the Investigator.

Sites should make every effort to target infusion timing to be as close to 30 minutes as possible. However, given the variability of infusion pumps from site to site, a window between -5 minutes and +10 minutes is permitted (i.e., infusion time is 30 minutes [-5 minutes/+10 minutes]).

ALKS 4230 may be infused using peripheral or central venous access per local standards of care and the treating investigator's judgement. All patients should have adequate intravenous access to allow the immediate management of toxicities. Subjects who do not have adequate peripheral venous access should have a central venous access device placed per local standards of care.

The amount of drug administered is based on subjects' body weight as measured at Day 1 (72 hours) of each cycle.

Sites must have written procedures in place detailing the healthcare personnel required to be on site during subject dosing, the availability of equipment and medications necessary to treat an emergency (should it occur) and the process for transferring a subject to a medical facility if necessary.

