3.8.2. Pembrolizumab Dosing and Administration

Pembrolizumab is to be administered as an IV infusion over 30 minutes in a dose of 200 mg every 3 weeks, in accordance with the prescribing information (Keytruda

Version V3.0

Syneos Health # 1006212

[pembrolizumab] USPI). Subjects will be monitored for at least 1 hour for potential acute reactions to pembrolizumab prior to administration of ALKS 4230.

Sites should make every effort to target infusion timing to be as close to 30 minutes as possible for either drug. However, given the variability of infusion pumps from site to site, a window between -5 minutes and +10 minutes is permitted for ALKS 4230 and pembrolizumab (i.e., infusion time is 30 minutes [-5 minutes/+10 minutes]).

Pembrolizumab is to be obtained from the study sites' pharmacies, from commercial supplies, or provided by Sponsor in countries where pembrolizumab is not yet approved.

Version V3.0

Syneos Health # 1006212

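### On Part C pembrolizumab days, the 60 (±30) minute window lets ALKS 4230 start before the required hour of monitoring for acute pembrolizumab reactions is over

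*Protocol*

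**What the plan says.** Two rules govern the gap between the drugs on days when both are given.

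- **The dosing window.** The synopsis states that "on days where ALKS 4230 is administered in combination with pembrolizumab, ALKS 4230 should be administered by infusion 60" (±30) minutes after pembrolizumab is completed. Protocol 9.1.1 gives the same window and counts it in "minutes after the completion of pembrolizumab infusion". SAP 3.8.1 repeats it: "ALKS 4230 should be administered as an infusion 60" (±30) minutes, counted from the same point.
- **The monitoring minimum.** Under Protocol 9.1.2 each subject is "monitored for at least 1 hour for potential acute reactions to pembrolizumab prior to administration of ALKS 4230, as described in Section 9.1.1". SAP 3.8.2 has the same requirement without the cross-reference: "Subjects will be monitored for at least 1 hour for potential acute reactions to pembrolizumab prior to administration of ALKS 4230".

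Protocol 9.1.2 does not say when the hour begins. Section 9.1.1, to which it points, describes no monitoring period; it contains only the window. Neither document ranks the two rules.

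In Protocol Table 7 the row "Administration of Pembrolizumab" is marked on Day 1 of each cycle only. Footnote d to that table sets the vital signs. On Day 1 of Cycles 1 and 2 they are taken before, during and at the end of pembrolizumab, and again before ALKS 4230. Later the schedule thins: "On dosing days in Cycles 3 and beyond, vital signs are to be collected before pembrolizumab infusion; middle of ALKS 4230 infusion".

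**The concern.** One rule is a symmetric tolerance around 60 minutes and the other is a floor at 60 minutes. A site that follows 9.1.1 is told that 30 minutes is acceptable, and can then give less observation than 9.1.2 requires.

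Three things are at stake.

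- **Safety.** From Cycle 3 no vital signs are scheduled between the reading before pembrolizumab and the middle of the ALKS 4230 infusion. In the Extension Phase vital signs are taken only every third cycle (Table 8, footnote c). The monitoring hour is then the main stated safeguard specific to that gap, and Part C dosing may be outpatient.
- **Deviations.** Protocol 8.6 requires deviations to be reported to the sponsor and included in the study report, and SAP 5.3 lists them. A start at 40 minutes complies with 9.1.1 and, on the natural reading, departs from 9.1.2. With up to 36 sites, monitors have no common rule.
- **Attribution.** Protocol 13.3 attributes Part C adverse events to both drugs unless the investigator states otherwise. Its own example of an exception is an event after pembrolizumab and before ALKS 4230. SAP 9.3 tabulates events by relationship to each drug separately. A shorter gap leaves less time in which a reaction can be assigned to pembrolizumab alone. This touches attribution, not the incidence of adverse events.

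**Working it through.** **Inputs**

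- ALKS 4230 window: 60 (±30) minutes from completion of pembrolizumab (synopsis; Protocol 9.1.1; SAP 3.8.1).
- Monitoring minimum: 60 minutes before ALKS 4230 (Protocol 9.1.2; SAP 3.8.2).
- Pembrolizumab infusion time: 30 minutes (−5/+10), so 25 to 40 minutes (Protocol 9.1.2; SAP 3.8.2).
- Cycle length in Part C: 21 days. Combination treatment is capped at 2 years (Protocol 8.1).

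**Permitted start, from the end of pembrolizumab**

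- Earliest: 60 − 30 = 30 minutes.
- Latest: 60 + 30 = 90 minutes.

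**Shortfall against the 60-minute minimum, at the earliest permitted start**

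Shortfall = max(0, 60 − observation time). Observation time is the gap alone if the hour runs from the end of the infusion, and infusion time plus gap if it runs from the start.

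| Hour runs from | Infusion (min) | Observation (min) | Shortfall (min) |
|---|---|---|---|
| End of infusion | any | 30 | 30 |
| Start of infusion | 25 | 25 + 30 = 55 | 5 |
| Start of infusion | 30 | 30 + 30 = 60 | 0 |
| Start of infusion | 40 | 40 + 30 = 70 | 0 |

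On the end-of-infusion clock every start from 30 to just under 60 minutes, the whole lower half of the window, is too early. On the start-of-infusion clock the conflict survives only for infusions shorter than 30 minutes.

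**How often the text applies**

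Pembrolizumab is given on 1 of the 5 ALKS 4230 dosing days per cycle. Under the 2-year cap, 730 / 21 = 34.8, or about 35 Day 1s per subject at most. This counts days on which the two rules apply, not expected breaches; the documents give no distribution of actual start times.

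**Check of the proposed window, 60 (+30) minutes after completion**

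- Clock from the end: the earliest start is at 60 minutes, so the minimum is met.
- Clock from the start: the shortest case is 25 + 60 = 85 minutes, so the minimum is met.

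**The case against.** The strongest reply is that the rules can be met together. The window is worded with *should* and the monitoring with *will*, so a mandatory floor limits an advisory window, and any start at 60 to 90 minutes, including the target, satisfies both. That is a reasonable way to resolve the conflict, but the documents do not state it. If it is what the sponsor intends, the −30 has no use on the end-of-infusion clock and should not be there.

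The second reply is that the 30-minute figure depends on an unstated clock. The cross-reference to 9.1.1 may refer only to how ALKS 4230 is given, and SAP 3.8.2 has no cross-reference at all. Counted from the start of a nominal 30-minute infusion, the earliest permitted start gives exactly 60 minutes. Vital signs during pembrolizumab in Cycles 1 and 2 fit that reading. This stands as a limit on the size of the problem: the mismatch is certain, but its extent is 5 or 30 minutes depending on the clock. The end-of-infusion clock remains more natural, because the only relevant interval in 9.1.1 is counted from completion.

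Third, other safeguards exist. In Cycles 1 and 2 vital signs are taken before ALKS 4230. In every cycle Protocol 9.1.1 calls for emergency resuscitation equipment, adequate intravenous access and written emergency procedures, and 9.2 refers infusion reactions to the pembrolizumab label. No safety event in the documents is tied to early starts. All of this is correct and tempers the concern. But these measures prepare for a reaction; they do not supply the observation period that 9.1.2 asks for.

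**Conclusion.** The concern holds. Two stated rules conflict, and a start that the window permits can break the monitoring minimum on either clock: by up to 30 minutes if the hour runs from the end of the pembrolizumab infusion, and by up to 5 minutes if it runs from the start. The larger figure rests on the end-of-infusion reading, which the text favours but does not state. The conflict is confined to Day 1 of combination cycles and does not bear on response rate, sample size or error rates. It is a safety and conduct point that should be corrected, because it leaves the observation time and the definition of a deviation to each site's choice of section.

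**What to change.** Change the window to 60 (+30) minutes after completion of the pembrolizumab infusion in the synopsis, Protocol 9.1.1 and SAP 3.8.1. State in Protocol 9.1.2 that the hour runs from the end of the infusion, and repeat this in SAP 3.8.2 for consistency. That gives one rule for dosing and one for deviations.

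The change is to wording only. The shortest permitted gap rises from 30 to 60 minutes, so subjects who would have started early spend up to 30 minutes longer in the chair. The 90-minute limit stays. The 60-minute target becomes the lower bound, so sites will in practice aim a little later to avoid deviations of a minute or two.

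There are alternatives. If the sponsor considers 30 minutes of observation sufficient, the minimum could be lowered to match the present window, but that weakens the safeguard and would need a clinical justification. Stating that the 1-hour minimum governs would also work once the clock is defined. Defining the clock alone would not, since a shortfall of 30 or 5 minutes would remain possible.
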